7. SAFETY REPORTING

7.1 Section 10 WMO event

In accordance to section 10, subsection 4, of the WMO, the sponsor will suspend the study if there is sufficient ground that continuation of the study will jeopardise subject health or safety. The sponsor will notify the accredited METC without undue delay of a temporary halt including the reason for such an action. The study will be suspended pending a further positive decision by the accredited METC. The investigator will take care that all subjects are kept informed.

7.2 AEs, SAEs and SUSARs

7.2.1 Adverse events (AEs)

Adverse events are defined as any undesirable experience occurring to a subject during the study, whether or not considered related to intranasal MSC treatment. All adverse events reported spontaneously by the subject or observed by the investigator or his staff will be recorded.

7.2.2 Serious adverse events (SAEs)

A serious adverse event is any untoward medical occurrence or effect that at any dose:

- results in death;
- is life threatening (at the time of the event);
- requires hospitalisation or prolongation of existing inpatients' hospitalisation;
- results in persistent or significant disability or incapacity;
- is a congenital anomaly or birth defect;
- Any other important medical event that may not result in death, be life threatening, or require hospitalization, may be considered a serious adverse experience when, based upon appropriate medical judgement, the event may jeopardize the subject or may require an intervention to prevent one of the outcomes listed above.

The sponsor will report the SAEs through the web portal *ToetsingOnline* to the accredited METC that approved the protocol, within 15 days after the sponsor has first knowledge of the serious adverse events.

SAEs that result in death or are life threatening should be reported expedited. The expedited reporting will occur not later than 7 days after the responsible investigator

has first knowledge of the adverse event. This is for a preliminary report with another 8 days for completion of the report.

7.2.3 Suspected unexpected serious adverse reactions (SUSARs)

Adverse reactions are all untoward and unintended responses to an investigational product related to any dose administered.

Unexpected adverse reactions are SUSARs if the following three conditions are met:

- 1. the event must be serious (see chapter 7.2.2);
- there must be a certain degree of probability that the event is a harmful and an undesirable reaction to the medicinal product under investigation, regardless of the administered dose;
- the adverse reaction must be unexpected, that is to say, the nature and severity of the adverse reaction are not in agreement with the product information as recorded in:
 - Summary of Product Characteristics (SPC) for an authorised medicinal product;
 - IB for an unauthorised medicinal product.

The sponsor will report expedited the following SUSARs through the web portal *ToetsingOnline* to the METC:

- SUSARs that have arisen in the clinical trial that was assessed by the METC;
- SUSARs that have arisen in other clinical trials of the same sponsor and with the same medicinal product, and that could have consequences for the safety of the subjects involved in the clinical trial that was assessed by the METC.

The remaining SUSARs are recorded in an overview list (line-listing) that will be submitted once every half year to the METC. This line-listing provides an overview of all SUSARs from the study medicine, accompanied by a brief report highlighting the main points of concern.

The expedited reporting of SUSARs through the web portal ToetsingOnline is sufficient as notification to the competent authority.

The expedited reporting will occur not later than 15 days after the sponsor has first knowledge of the adverse reactions. For fatal or life threatening cases the term will be maximal 7 days for a preliminary report with another 8 days for completion of the report.

7.3 Annual safety report

In addition to the expedited reporting of SUSARs, the sponsor will submit, once a year throughout the clinical trial, a safety report to the accredited METC and competent authority.

This safety report consists of:

- a list of all suspected (unexpected or expected) serious adverse reactions, along with an aggregated summary table of all reported serious adverse reactions, ordered by organ system, per study;
- a report concerning the safety of the subjects, consisting of a complete safety analysis and an evaluation of the balance between the efficacy and the harmfulness of the medicine under investigation.

7.4 Follow-up of adverse events

All AEs will be followed until they have abated, or until a stable situation has been reached. Depending on the event, follow up may require additional tests or medical procedures as indicated, and/or referral to the general physician or a medical specialist. SAEs need to be reported until discharge after the second MRI around the age of 3 months. As described in chapter 7 of the IB, MSCs do not survive for a very long period. When MSCs disappear within a short time frame and they are no longer present in the subject, they are not able/unlikely to lead to (serious) adverse events such as death, tumor formation or disturbances of the immune system. We have therefore decided that after a period of 3 months, AE or SAEs are very unlikely to be linked to the use of MSCs and conclusions regarding safety of MSCs can be drawn.

7.5 Data Safety Monitoring Board (DSMB)

A DSMB will be established to perform ongoing safety surveillance and to perform interim analyses on the safety data. This committee will be an independent committee. The DSMB is composed of 4 members from the UMCU: three are members of the internal DSMB of the UMCU and one member has clinical expertise as paediatric neurologist. Each member has no conflict of interest with the study. The task and responsibility of the DSMB are described in the DSMB charter. CVs of each DSMB member are added to the DSMB charter.

The DSMB may decide to terminate the trial prematurely using the stopping criteria as stated in chapter 6.7 of this protocol.

The advice(s) of the DSMB will only be sent to the sponsor of the study. Should the sponsor decide not to fully implement the advice of the DSMB, the sponsor will send the advice to the reviewing METC, including a note to substantiate why (part of) the advice of the DSMB will not be followed.

8. STATISTICAL ANALYSIS

In this study, 10 newborns will be included who will be treated with MSCs via the nasal route. This is a phase I/II, open-label, single-arm, single-center intervention study to assess the safety and feasibility of intranasal BM-MSCs in neonatal stroke patients.

8.1 Study parameter(s)

Safety is defined primarily as the absence of treatment-related serious adverse events (SAEs) according to the Consolidated Standards of Reporting Trials (chapter 7.2 and bron), secondly as the absence of dose-limiting toxicity, defined as death within 24 hours after MSC transplantation or anaphylactic shock related to the MSC administration, and thirdly as the absence of adverse events at 3 months of age in terms of cerebral damage and neurodevelopmental outcome (see secondary outcome).

For acute safety, all vital signs and blood sample parameters (continuous variables) at baseline and at 24 hours following MSC transplantation will be compared using Wilcoxon signed-rank tests. The occurrence of SAE's, including mortality, toxicity, tumor growth, etc (see chapter 11.1) will be expressed in percentages and analyzed qualitatively.

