However, the results from adult trials can be used to support safety and feasibility of MSC treatment in neonatal stroke. Clinical trials with MSC treatment for adult patients with ischemic stroke have shown some evidence for the efficacy of MSCs in the treatment of ischemic stroke. These studies described patients who were treated with MSC at 7-133 days post-stroke.(Bang et al. 2005; Honmou et al. 2011) Although the evidence is sparse, there are some trials, mainly uncontrolled open-label studies, that have demonstrated clinical neurological improvement in patients with acute and chronic stroke after treatment with MSCs.(Bang et al. 2005; Lee et al. 2010) Most importantly, these trials have not demonstrated any serious adverse events, such as neurological deterioration, systemic infections nor tumor development, related to MSC transplantation. This is also concluded from a meta-analysis on over 1200 patients treated with MSCs for various pathological indications. Only transient fever within the first days seemed to be related to MSC transfusion.(Lalu et al. 2012)

There is only one clinical trial describing the use of MSCs in treatment of neonates.(Chang et al. 2014) Chang et al. assessed in a phase I dose-escalation trial the safety and feasibility of intratracheal administration of allogeneic umbilical cord-derived MSCs in preterm infants with high risk for bronchopulmonary dysplasia (BPD). Importantly, there were no serious adverse events or toxicity related to a higher dose of 2 x 10⁴7 cells/kg.(Chang et al. 2014) These

findings were more recently confirmed by another group treating 3 premature infants with approximately 2 x 10⁶/kg bone marrow-derived MSCs intravenously.(Henckel et al. 2015) The authors concluded that intravenous MSC treatment was feasible, well tolerated and no effects on pulmonary and cerebral blood flow could be detected.(Henckel et al. 2015) An ongoing study in Korea is treating preterm infants with intraventricular hemorrhage with allogeneic umbilical cord MSCs, and preliminairy results are promising and show no adverse effects.(Presented at Pediatric Academic Societies Meeting, Baltimore, Monday May 2, 2016 - 8:00 am, E-PAS2016:3090)

Overall, MSC treatment under several pathologic conditions, including stroke, in adults and children appeared to be safe.

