5.4 Summary of known and potential risks and benefits

An overview of findings on potential risks and benefits of MSC treatment for PAIS is given in chapters 7 and 8 of the IB.

In summary, we have shown in our own mouse models of neonatal ischemic infarction that intracerebral application of murine adult bone marrow-derived MSCs markedly improves outcome. Treatment with MSC reduced infarct size by >45%, stimulated formation of new neurons and oligodendrocytes, partially restored cortico-spinal motor tract activity, and improved sensorimotor outcome.(van Velthoven et al. 2010c; van Velthoven et al. 2010a) Additionally, our findings indicate that MSCs can be successfully and rapidly administered to the brain via an efficient non-invasive route, the nasal route.(Donega, van Velthoven, Nijboer, van Bel, et al. 2013) The MSCs subsequently accumulate predominantly in the infarcted area. Notably, MSCs delivered via the nasal route reduce infarct size and improve motor function to the same extent as MSCs administered intracranially.(van Velthoven et al. 2010b)

In general, risks or adverse events related to MSC treatment can be categorized in three groups: acute, subacute and longterm adverse events.

- 1. Acute adverse events: Administration Reaction/Toxicity
 - Systolic blood pressure >33% decrease or increase from the baseline during or directly following the intranasal administration of the investigational product
 - Diastolic blood pressure >25% decrease or increase from baseline during or directly following the intranasal administration of the investigational product
 - Heart rate >33% decrease or increase from baseline during or directly following the infusion of the investigational product
 - Development of dyspnoea, vomiting, flushing, diarrhea, during or within 1 hour from the intranasal administration of the investigational product
 - Fever ≥ 2 grade increase from baseline during or within 2 hours from the intranasal administration of the investigational product
 - Development of exanthema, or urticaria developing during or within 2 hours from the intranasal administration of the investigational product

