From animal models of neonatal stroke we can conclude that no adverse effects have been described for MSC treatment. Our research group has also assessed long-term safety of intranasal MSC treatment. (Donega et al. 2015) At 14 months following HI no significant lesions or neoplasia were observed in the nasal tubinates, brains or other peripheral organs of mice treated intranasally with MSCs. Additionally, it has been shown that MSCs improved sensorimotor and cognitive function for at least 9 and 14 months, respectively. These results provide strong evidence of long-term safety (and efficacy) of MSC treatment following neonatal HI in mice. (Donega et al. 2015) Also a large metaanalysis on MSC treatment for various pathologies does not support tumorigenicity of MSC.(Lalu et al. 2012) Table 1 from the IB summarizes several other studies that performed administration of autologous and allogenic bone marrow derived MSCs in the treatment of several diseases. From these studies with a follow-up time of 2 months to 4 years, it was shown that (adult) patients do not have an increased risk of long-term effects, including tumorigenicity, after allogeneic MSC treatment.

Risk-benefit balance

We can conclude that MSC treatment in newborns with PAIS might be beneficial and no subacute and long-term risks are to be expected based on available evidence. Acute administration reactions, such as subacute temperature increases, are potentially to be expected, but these are expected to be transient, self-limiting and unharmful, based on the available evidence. However, this is the first study in which MSCs will be administered intranasally in humans, so potential risks might be unknown and/or unexpected. Therefore we have planned to perform a pilot (phase I/II) trial to assess safety and feasibility of MSC treatment in newborns with PAIS. Using close monitoring and (preventative) planned actions, as described in chapter 11.1e and 11.2, and tightly regulated stopping rules (see chapter 6.7) we expect to minimize or prevent risks.

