As described in chapter 8 of the IB, there are many other clinical trials in adults in which MSC are used for the treatment of several diseases. Although the hypothesized mode of action of MSCs in different pathological conditions varies, the most important findings from these clinical trials refer to safety issues. In none of the trials serious adverse events related to MSC treatment were detected during bone marrow harvesting and administration. Some studies reported mild allergic reaction(Duijvestein et al. 2010), probably related to preservation substances in the MSC-product, or self-limiting fever within a few hours after MSC-transplantation. (Shi et al. 2012) In some studies patients had a serious adverse event, most likely not related to MSC administration. (Forbes et al. 2014; Wang et al. 2013; Weiss et al. 2013; Haack-sørensen et al. 2014) Additionally, a large meta-analysis on clinical trials for numerous diseases did not show any evidence for severe adverse effects due to MSC transplantation.(Lalu et al. 2012) This analysis used both adult and pediatric trials to report on a total of 1012 patients with ischemic stroke, Crohn's disease, cardiomyopathy, myocardial infarction, GvHD and healthy volunteers. Including eight randomized control trials, there was no association detected between MSC transplantation and acute infusional toxicity, organ system complications, infection, death or malignancy. There was a significant increase in fever with MSCs compared to the control group, but the fever was reported to be transient in all trials and most often low grade (≤38°C).(Lalu et al. 2012)

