No correlation between the dose of MSC and their potential efficacy or side effects could be observed in multiple studies (range 1-8 10^6 cells/kg body weight).(Lalu et al. 2012) It is known that systemic complications such as fever are more common when MSCs were systemically (e.g. intravenously) administered. We found no evidence that fever occurred in our animal studies.(Donega et al. 2015) From our preclinical studies in mice we found that local (intracranial) administration of MSCs at 3 days after brain injury resulted in a decrease of pro-inflammatory cytokines IL-1 β , IL-1R and IL-3.(van Velthoven et al. 2011)In vitro we have also found that if MSCs are cultured in a hypoxic-ischemic brain environment, they produce more growth factors and less pro-inflammatory cytokines (IL-1 β , IL-6 en TGFb) than MSCs cultured in a normal brain environment.(van Velthoven et al. 2010b) Intranasal administration of MSCs, dampened neuro-inflammatory responses due to hypoxic-ischemic brain injury at 5-18 days after MSC treatment. The number of GFAP and Iba-1 positive cells, as markers for the neuroinflammatory response of glial cells, decreases after administration of MSCs, possibly as a result of anti-inflammatory

functions of MSCs. (Donega, Nijboer, van Tilborg, et al. 2014) In conclusion, it seems that local/nasal MSC treatment has rather an anti-inflammatory effect and will not induce inflammation. We therefore do not expect fever to complicate intranasal administration of MSCs, as a priori chances are low. Additionally, the danger of transient and low grade fever is low.

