11.2 Synthesis

Adverse events, observed by the attending physician, which are expected or possibly related to the infusion of the product, are reported to the head of the CTF. Adverse events will be reported in a database, including patient characteristics and product characteristics. Adverse events will be evaluated with the Medical Director of the CTF in their weekly meetings. We will report the observed adverse events to the Dutch Health Inspectorate. Serious adverse events will be reported within 48 hours after the event has happened.

Planned pharmacovigilance actions for potential risks

1. Acute adverse effects: Administration Reaction, during and shortly after administration Planned actions:

 Monitoring of heart rate and blood pressure. And development of dyspnoea, nausea/vomiting, flushing, diarrhea, during or within 1 hour from the administration of the investigational product

- Monitoring temperature during or within 2 hours from the administration of the investigational product. During admission, temperature will be monitored very strictly, because hyperthermia after hypoxia-ischemia is associated with adverse (neurologic) outcome.(Laptook et al. 2008; Perlman 2006) If the temperature rises above 37.5°C we will use routinely clinical used precautions to prevent actual hyperthermia, such as lowering environmental temperature or use paracetamol.
- Development of exanthema or urticaria developing during or within 2 hours from the administration of the investigational product.

2. Subactue adverse effects:

Bacteremia due to bacterial contamination of product.

Planned actions: Monitoring of temperature during the following hours to days after intranasal administration. In case of contamination patients will be treated with antibiotics in case this is required.

Systemic infection due to use of MSC therapy

Planned actions: Close monitoring of first three patients by extra blood sampling and determination of infection markers. In case of systemic infection patients will be treated with appropriate antibiotics in case this is required, according to the antibiotics protocol used on the NICU.

• Post-administration virus infection.

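### Section 8.1 compares vital signs only at baseline and 24 hours, so a short, low-grade temperature rise after dosing may not show in the planned analysis

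*Combined protocol and SAP*

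**What the plan says.** Section 8.1 states that "all vital signs and blood sample parameters (continuous variables) at baseline and at 24 hours following MSC transplantation will be compared", using Wilcoxon signed-rank tests. It also summarises SAEs, including toxicity, as percentages, with a pointer to chapter 11.1. Section 8.2 adds nothing. No section names an analysis of readings between baseline and 24 h.

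On fever after MSCs, the protocol says:

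- Section 11.1e, on a meta-analysis that found more fever with MSCs than with control: "the fever was reported to be transient in all trials and most often low grade (≤38°C". One further study is cited there for "self-limiting fever within a few hours after MSC-transplantation".
- Introduction and Rationale, on the same meta-analysis: "Only transient fever within the first days seemed to be related to MSC transfusion".
- Section 5.4 (risk-benefit balance), on acute reactions in this trial: "such as subacute temperature increases, are potentially to be expected, but these are expected to be transient, self-limiting and unharmful".
- Section 11.1e, on the nasal route: "We therefore do not expect fever to complicate intranasal administration of MSCs".
- Section 11.2: "If the temperature rises above 37.5°C we will use routinely clinical used precautions to prevent actual hyperthermia". The measures named are a cooler environment or paracetamol.
- Sections 5.4 and 11.1e list as an administration reaction: "Fever ≥ 2 grade increase from baseline during or within 2 hours from the intranasal administration of the investigational product". The word grade is not defined.

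Section 6.3 has vital signs monitored intensively from baseline to at least 24 h after treatment. Section 7.2.1 has all observed adverse events recorded.

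**The concern.** Fever is the one effect that the cited meta-analysis links to MSCs. It is described as short and low grade, and the plan treats it at the bedside. The only planned comparison that could show it uses a single reading taken a day later. By then the rise may be over, or treatment may have lowered it.

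At stake is a supportive statement in the report. A line saying that vital signs did not change could be printed although several infants had a rise after dosing. Section 1 names vital signs in the acute-safety objective. Section 11.2 links hyperthermia after hypoxia-ischaemia to worse neurological outcome. The protocol also both anticipates temperature rises (5.4) and says that fever is not expected by this route (11.1e). A first-in-human intranasal study should be able to describe what happened, and the readings after dosing are already taken.

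**Working it through.** The plan gives no power or detection figure for this comparison, so there is none to reproduce. The documents supply n = 10, the two time points, the test, the 37.5°C trigger, the 38°C description and the 2-grade, 2-hour reaction. They do not supply temperature variability, the size or duration of a rise, the reading frequency, or the alpha. These are assumed below, with two-sided 5% for alpha.

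**1. Does the listed fever reaction fill the gap?** If grade means °C, a peak of 38.0°C qualifies only from a baseline of 38.0 − 2 = 36.0°C or lower, and a peak of 37.6°C only from 35.6°C or lower. Assume a baseline reading with mean 37.0°C and SD √(0.2² + 0.2²) = 0.28°C. The chance of a baseline at or below 36.0°C is then Φ(−1.0/0.28) ≈ 0.0002. With a mean of 36.8°C it is about 0.002. A rise from 37.0 to 38.0°C passes the treatment trigger but is only half the reaction threshold. If grade means something else, such as a severity grade, this step cannot be done from the text.

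**2. How much of a rise is left at 24 h?** For a peak at 2 h that decays exponentially with half-life h, the remainder is peak × 0.5^(22/h). For peaks of 0.5 to 1.0°C:

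- h = 2: below 0.001°C
- h = 4: 0.01 to 0.02°C
- h = 8: 0.07 to 0.15°C

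**3. What does the 24 h test detect?** The exact signed-rank test at n = 10 rejects at T ≤ 8, with size 50/1024 = 0.0488. Simulated inputs: infant means N(37.0, 0.2²), reading SD 0.2, a reading every 3 h, and seven infants with a 0.8°C rise from the first reading. Treatment starts after the first value above 37.5°C and removes none, half or all of the remaining rise.

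| Course of the rise | Untreated rise left at 24 h | No treatment | Half removed | All removed |
|---|---|---|---|---|
| Half-life 4 h | 0.02°C | 5% | 5% | 5% |
| Half-life 8 h | 0.13°C | 13% | 7% | 5% |
| Half-life 12 h | 0.24°C | 31% | 13% | 5% |
| Half left at 24 h | 0.40°C | 63% | 25% | 5% |

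Repeat runs agree within about one percentage point. Timing is the main weakness. Treatment adds to it only when the rise lasts.

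A second model (peak at 2 h, SD of change 0.3 to 0.5°C, peak 0.5 to 1.0°C, 30 to 100% of infants affected) gives about 5% at 24 h for half-lives of 2 to 4 h, and 5 to 28% for 8 h. The same test at 2 h would detect 78% to more than 99% if all infants react, 23 to 58% if half do, and 12 to 25% if 30% do.

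**4. What would a count show?** With the inputs of step 3, a 4 h half-life and no treatment, the mean number of infants above 37.5°C in the 24 h after dosing is 2.5, 3.2, 3.9 and 6.7 of 10 with 1, 2, 3 and 7 reactors. In 24 h without any effect it is 1.8. That background moves with the assumed mean: 0.4 at 36.8°C and 4.7 at 37.2°C. It also moves with reading frequency: 1.2 with 4 readings a day and 3.1 with 24. The count is informative as a description, but it has no fixed reference level.

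**5. Should a formal before-and-after test of the highest temperature be added?** Comparing equal 24 h windows detects 96% with seven reactors (4 h half-life), but only about 5 to 18% with one to three. It also needs a neutral pre-dose day. Before dosing an infant may have acute symptoms, transfer (2.4) and a sedated MRI (6.1.2). With no MSC effect and pre-dose readings 0.2°C lower throughout, that test is significant in 88% of simulated trials. With seven reactors and a similar pre-dose rise in the other three infants, detection falls from 96% to about 3 to 4%. A formal test is therefore not recommended.

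**The case against.** The strongest reply is that the signed-rank test is not the only route by which fever is assessed. Sections 1 and 2.1 say that adverse events will be assessed. Section 7.2.1 defines them broadly and has all observed ones recorded, and a rise that prompts paracetamol plausibly qualifies. Section 11.2 watches temperature in the first 2 h and again over the following hours to days. Section 11.1e judges low-grade fever to be of little danger, and 5.4 expects rises to be harmless. Fever is not among the effects listed in the stopping rules of 6.7. Fever may also still be present at 24 h, since the Introduction speaks of the first days. Finally, no text says that temperature is one of the vital signs in 8.1.

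Most of this stands, and it limits importance. It does not close the gap. No text names a rise to 37.6–38.0°C as an adverse event, and 8.1 specifies no summary of non-serious events apart from its pointer to chapter 11.1. If temperature is not a vital sign for 8.1, then 8.1 contains no temperature comparison at all, and the same addition is needed. A longer fever is covered in the last row of the table: 63% detection untreated, and 25% or 5% with effective treatment.

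A reader might infer that fever would go unnoticed, that infants would be at risk, or that the trial's safety conclusion is unsound. The documents support none of these. Bedside monitoring is close, and safety is defined primarily by treatment-related SAEs. Nor do they show that a rise will occur. Seven reactors of ten is an illustration without a source in the documents.

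**Conclusion.** The point holds as a minor gap in a supportive analysis. Followed as written, 8.1 can report no change in temperature after a real, short, low-grade rise. Under the assumed inputs, detection is 5% for a 4 h half-life and up to 63% for an untreated rise still half present at 24 h. The size rests wholly on assumed variability, size and duration of the rise. The direction rests on the protocol's own description of the fever as transient and on its treatment trigger. Two readings of the text are also assumed: that vital signs include temperature, and that grade means °C.

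The finding concerns what is analysed, not what is observed or how infants are cared for. It is not a claim of bias in heart rate, blood pressure or infection markers, and it leaves the SAE-based primary conclusion and the stopping rules as they are.

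**What to change.** In 8.1, keep the 24 h comparison and add a descriptive summary of temperature:

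- For each infant, list the highest temperature and the largest change from baseline over 0–2 h and over 0–24 h after dosing.
- Give the number of infants above 37.5°C, and the number started on or increased in paracetamol or active cooling.
- Show pre-dose chart values and pre-dose treatment alongside where available, as context only.
- State whether the 2-grade fever criterion means °C, and whether vital signs in 8.1 include temperature.

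Do not add a formal before-and-after test, for the reasons in step 5 of the working.

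The cost is a few sentences of protocol text and some chart transcription. Section 6.3 already covers monitoring from baseline to at least 24 h, so no new procedure is needed and bedside care does not change. Section 6.3 does not guarantee a full pre-dose day of readings, which is why those values are context only. With ten infants, no control arm and an uncertain pre-dose background, the listing can describe temperature after dosing but cannot attribute a rise to the cells.
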